## **12** Statistical Analysis

# 12.1 Analysis of data/ study outcomes

The studies performed under this protocol are exploratory. Quantitative research data will be acquired and logged into a database. The PI or designated investigator will monitor data integrity. Because a variety of types of data will be obtained in the study, the statistical methods most appropriate for the nature of the data will be used. Some of the relevant statistical approaches are as follows:

We are primarily interested in evaluating whether various types of data obtained are significantly different between the three groups as measured in cross-section during the phenotyping visit as well as between HV and PI-ME/CFS groups before and after an exercise stress. Each of these groups will be characterized using standard descriptive statistical methods.

As noted in Section 4.5, ME/CFS participants that are found no to meet the strict inclusion/exclusion of this study all have been diagnosed with ME/CFS by health providers and represent ME/CFS in the community. HVs and COVID-19 HVs that do not have fatigue or PEM may also be found to medical issues or other findings that would exclude them from meeting the strict inclusion/exclusion criteria of being healthy, but still represent a non-fatigue comparator to ME/CFS patients. The primary focus of the analyses detailed below will be between adjudicated ME/CFS participants and HVs and COVID-19 HVs that meet all inclusion/exclusion criteria. If the result of a primary analysis is positive, a secondary analysis will be repeated using all of participants. Findings that remain robust even when less stringent inclusion/exclusion criteria are used suggest that they are more likely to be replicable in community cohorts and perhaps worthy of further exploration.

For each continuous-scale outcome, repeated measures analysis of variance (ANOVA) will be used to test whether there are significant differences in cross-sectional measurements as well as in the pre and post measurements among two groups by using F tests. These initial tests will be performed using the adjudicated PI-ME/CFS group (i.e. participants determined to have PI-ME/CFS by the protocol's adjudication process) compared to HV and COVID-19 HV participants meeting all inclusion and exclusion criteria. The cross-sectional analyses may then be repeated using all HV and COVID-19 HV participants that did not report substantial clinical fatigue as noted above.

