If the overall multivariate test is significant, we will follow up with several post-hoc tests. Specifically, we will first conduct multivariate tests to compare the adjudicated PI-ME/CFS group (i.e. participants determined to have PI-ME/CFS by the protocol's adjudication process) vs the other two control groups, and the PI-ME/CFS group vs each of the two control groups. These analyses will initially performed using only HV and COVID-19 HV participants meeting all inclusion and exclusion criteria. As noted above, for analyses that are statistically significant, the analysis will be repeated using all HV and COVID-19 HV participants that did not report substantial clinical fatigue to determine if the results remain statistically significant when less stringent inclusion/exclusion criteria are applied.

Second, univariate ANOVA will be used for both cross-sectional measurements and pre and post exercise measurements separately to identify differences among groups. A
similar univariate analysis will be conducted for the measurements of change from pre- to post exercise using the univariate ANOVA.

Additionally, descriptive statistics will be used to characterize the entire group of ME/CFS participants that completed the phenotyping evaluation regardless of adjudication. Comparisons will be made between the adjudicated PI-ME/CFS group and the phenotyping ME/CFS group. If there is no significant difference between the above two groups, it is not necessary to compare a ME/CFS group to our two control groups. Where statistically appropriate, the ANOVA methods described above will be used to compare the ME/CFS group with the two control groups.

Statistical approaches such as chi-square tests and multinomial logistic regression models will be used to examine the group differences for categorical outcomes.

A level of significance is set at 0.05. Multiple comparison test procedures such as Bonferroni and Dunnett's methods will be used to examine the differences in each outcome measure among groups.

The primary MRI imaging aim is to test whether PI-ME/CFS group has significantly different connectivity patterns compared to the HV control group.

To this end, functional MRI measures will be taken at three conditions: 1) performing a force task, 2) performing a cognitive task, to define a network of interest, and 3) at rest to compute functional connectivity. At each condition, fMRI will be measured at two time points: pre exercise (preEx) and post exercise (postEx).

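### Section 12.1 lets a non-significant difference between adjudicated cases and the phenotyped ME/CFS group stand as a reason to omit the formal comparison of the wider ME/CFS group with controls

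*Combined protocol and SAP*

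**What the plan says.** Section 12.1 sets the main contrast first: "The primary focus of the analyses detailed below will be between adjudicated ME/CFS participants and HVs and COVID-19 HVs" who meet all criteria. It then adds that "If the result of a primary analysis is positive, a secondary analysis will be repeated using all of participants", and that findings which survive the looser criteria "suggest that they are more likely to be replicable in community cohorts". When the repeat is described again two paragraphs later, for statistically significant analyses, only controls are named: "the analysis will be repeated using all HV and COVID-19 HV participants that did not report substantial clinical fatigue".

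A later paragraph of Section 12.1 turns to the wider patient group. Descriptive statistics will cover the "entire group of ME/CFS participants that completed the phenotyping evaluation regardless of adjudication". Next comes "Comparisons will be made between the adjudicated PI-ME/CFS group and the phenotyping ME/CFS group", and then the rule at issue: "If there is no significant difference between the above two groups, it is not necessary to compare a ME/CFS group" with the controls. The sentence after it reads: "Where statistically appropriate, the ANOVA methods described above will be used to compare the ME/CFS group with the two control groups".

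The section gives no equivalence margin, interval criterion or named test for the comparison of the two ME/CFS groups. It does not say which outcome or outcomes decide the matter. The significance level is 0.05, with sidedness not stated.

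Section 3.1 describes a different pairing. There, participants who fail the exercise-stress criteria act as a control group for those who qualify, so the two sets do not overlap. Sections 3.1 and 4.5 give the reason for keeping the former: they represent the illness as it is diagnosed in the community.

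**The concern.** A non-significant test says that the data do not rule out a zero difference. It does not say that the difference is small. With group sizes chosen for convenience (Section 12.2) and no power stated for this comparison, non-significance may be the likely result even when the subgroups differ by an amount that matters. If the rule is applied, the adjudicated result stands in for the wider group without a formal comparison of that group with controls.

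This matters because the protocol keeps non-adjudicated participants through phenotyping in order to learn about community ME/CFS, and because the results are meant to supply effect sizes for a larger study (Section 12.2). If the excluded participants resemble controls more than the adjudicated cases do, the adjudicated effect overstates the wider one.

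There is also a wording conflict. Section 12.1 describes the comparator as everyone phenotyped, which contains the adjudicated cases, while Section 3.1 implies separate groups.

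**Working it through.** **The plan's own figure.** There is none for this comparison. The only power statement, in Section 12.2 (12 subjects, 80% power, threshold 0.05), concerns single-voxel fMRI activation. It gives no effect size, so it cannot be reproduced or carried over.

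**Inputs.** From the documents: the 0.05 level; a target of 20 completers per group (Section 3.1); a ceiling of 50 per group (Section 12.2). Assumed: two-sided testing; equal SD; *k* = 20 adjudicated; *N* = 50, 40 or 30 phenotyped; separate groups of *k* and *N* − *k*; differences in SD units.

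**How often a real difference is missed.** The standard error in SD units is √(1/*k* + 1/(*N* − *k*)). The miss rate comes from the noncentral t distribution with *N* − 2 degrees of freedom and noncentrality *d*/SE. The 95% CI half-width is t(0.975, *N* − 2) × SE. For 20 against 30: SE = √(1/20 + 1/30) = 0.289; noncentrality at 0.5 SD = 0.5/0.289 = 1.73; half-width = 2.011 × 0.289 = 0.58.

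| Adjudicated of phenotyped | Missed at 0.5 SD | Missed at 0.8 SD | 95% CI half-width |
|---|---|---|---|
| 20 of 50 | 60% | 23% | 0.58 SD |
| 20 of 40 | 66% | 31% | 0.64 SD |
| 20 of 30 | 76% | 49% | 0.79 SD |

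The picture is similar if more are adjudicated: 30 of 50 gives 60% and 23%, and 40 of 50 gives 72% and 40%. With 20 adjudicated, even an observed difference of exactly zero would leave true differences of 0.58 to 0.79 SD inside the interval.

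**What the omission would hide: an example.** Suppose adjudicated cases differ from HV by 0.8 SD and the other ME/CFS participants by 0.3 SD. The wider group's true difference is [0.8*k* + 0.3(*N* − *k*)]/*N*. For 20 of 50 this is (16 + 9)/50 = 0.50 SD; for 20 of 40, (16 + 6)/40 = 0.55 SD; for 20 of 30, (16 + 3)/30 = 0.63 SD. The gap between subgroups is 0.5 SD, so the rule allows the wider comparison to be omitted in 60%, 66% and 76% of studies.

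**The same example with the repeat of positive analyses.** If that repeat brings in non-adjudicated ME/CFS participants, the wider comparison is lost only when the adjudicated-versus-HV test is also non-significant. Simulation (100,000 studies per setting, normal data, pooled t tests, HV number assumed, COVID-19 HV not modelled) gives both tests non-significant in about 26 to 28% of studies with 20 HV and about 14 to 15% with 50 HV. As a check, the adjudicated-versus-HV test at 0.8 SD misses in 31% of studies (20 v 20) and 15% (20 v 50), and the joint rate cannot exceed those. It exceeds the product of the two rates (0.60 × 0.31 = 0.19 for 20 of 50 with 20 HV) because a low adjudicated mean makes both tests non-significant.

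**The overlap wording.** For a subset of *k* within a whole of *N*, the true variance of the difference in means under no difference is σ²(1/*k* − 1/*N*), whereas an independent-samples test assumes σ²(1/*k* + 1/*N*). For 20 within 50 the SE ratio is √(0.03/0.07) = 0.655, so a nominal 5% test has a size of about 2P(Z > 1.96/0.655) = 0.3%. Such a test would be strongly conservative and would favour the result that permits the omission. This is conditional, because no test is named.

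**The case against.** The strongest reply is that little hangs on the sentence, and much of that reply stands. The study is exploratory. The adjudicated-versus-control comparison does not pass through this rule. The rule waives a comparison without forbidding it, and the next sentence provides for one.

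A reader might infer that the wider group would be left with no estimate at all. The documents do not support that: the same paragraph plans descriptive statistics for everyone phenotyped, whatever the test shows. Only the formal comparison is at risk.

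A reader might also take 60 to 76% as the unconditional rate of loss in the example. That holds only if the repeat of positive analyses leaves out non-adjudicated ME/CFS participants. The paragraph that introduces the repeat opens with those participants and ends on community replicability, so it probably includes them. The later restatement names only HV and COVID-19 HV, so the ambiguity is real, but restating part of a rule does not cancel the rest.

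Nor do the figures show that large differences are usually missed. At 0.8 SD the miss rate nears one half only in the smallest split. The overlap problem stays hypothetical, since Section 3.1 points to separate groups.

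What the reply does not remove is the rule itself. The sentence that permits the ANOVA gives no criterion for when it is appropriate, so the choice can be made after results are seen. On the inclusive reading, the repeat still does not cover primary results that are not positive.

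**Conclusion.** The point holds, within limits. Section 12.1 contains a wrong rule, and this is more than a missing detail: an unpowered non-significant result is accepted as grounds for omitting a formal comparison. In every split examined, a 0.5 SD difference between the ME/CFS subgroups is more likely than not to go undetected (60 to 76% of studies). In the assumed 0.8 and 0.3 SD example, the formal comparison of the wider group with controls may be lost in 60 to 76% of studies on the narrow reading of the repeat, and in about 14 to 28% on the inclusive reading.

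These figures rest on assumed numbers adjudicated, assumed HV numbers, assumed effects, equal SDs and two-sided testing. If the two subgroups are truly alike, the rule costs only the separate formal comparison. It would be wrong to conclude that the primary analysis is compromised or that the wider comparison is prohibited. The sentence should be fixed, but no primary conclusion depends on it.

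**What to change.** In Section 12.1:

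- Delete the sentence that makes the wider comparison unnecessary after a non-significant result.
- Define the within-ME/CFS comparison as adjudicated cases against phenotyped participants not adjudicated as cases, in line with Section 3.1, and report the difference with its 95% CI.
- Run the comparison of the whole phenotyped ME/CFS group with the control groups as a labelled secondary analysis, whatever the within-ME/CFS result.
- Reconcile the two descriptions of the repeat analysis by stating whether it adds non-adjudicated ME/CFS participants or only the HV and COVID-19 HV participants who miss the strict criteria.

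The cost is rewording and a little more analysis on data already planned. Estimates for the smaller, separate group of non-adjudicated participants will be less precise, and the interval will show that openly.

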### 3.2.3 Additional inclusion criteria for participants with PI-ME/CFS for the exercise stress visit

1. Be unanimously considered to be a case of PI-ME/CFS by the protocol's adjudication committee.

2. Meet the 1994 Fukuda Criteria OR the 2003 Canadian Consensus Criteria for Myalgic Encephalomyelitis/Chronic Fatigue Syndrome OR the Institute of Medicine Diagnostic Criteria.

3. Have moderate to severe clinical symptom severity:

- Severe fatigue as determined using the Multidimensional Fatigue Inventory (MFI): score of ≥ 13 on the general fatigue subscale or ≥10 on the reduced activity subscale.
- Functional impairment as determined using the Short-Form 36 (SF-36): score of ≤70 physical function subscale, or ≤50 on role physical subscale, or ≤75 on social function subscale

*3.2.4 Additional inclusion criteria for healthy volunteer group None* 

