# 3.3.3 Additional exclusion criteria for participants with PI-ME/CFS for exercise stress visit

1. Current (within 1 week) use of prescription or over-the-counter medications, herbal supplements, or nutraceuticals that may influence brain excitability that the potential participant is either unwilling or clinically unable to safely wean off for the duration of the period of the exercise stress visit. The possibility for a potential participant to be weaned off medication will be cooperatively determined by both the clinical investigative team and personal physicians. Examples of medications that influence brain excitability include tricyclic antidepressants, hypnotic, antiepileptic, antipsychotic medication, stimulants, antihistamines, muscle relaxants, dopaminergic medications, and sleep medications.

3.3.4 Additional exclusion criteria for healthy volunteer group

- 1. Substantial daily fatigue as determined using PROMIS-SF Fatigue: score of > 17.
- 2. Significant neurological disorder (e.g. neurodegenerative disorder, stroke, epilepsy).
- 3. Current (within 1 week) use of prescription or over-the-counter medications, herbal supplements, or nutraceuticals that may influence brain excitability

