#### 4.5 Phenotyping Visit (Visit 1: Phenotyping)

The phenotyping visit will take place at the NIH Clinical Center up to 12 months before the exercise stress visit and is expected to last 5 days for HV and COVID-19 HV participants and 10 days for PI-ME/CFS participants. Phenotyping may occur on either an outpatient or an inpatient admission basis, depending on convenience. Information collected during the phenotyping visit will be used to determine PI-ME/CFS case status as well as to determine eligibility for the exercise stress visit. All procedures are for research purposes.

Consent will be obtained before any study procedures, including screening procedures, are done. Eligibility criteria will be reviewed during the consent process. An eligibility criteria checklist will be reviewed on Visit 1 completion and documented in the protocol's research records.

CNS IRB Protocol Template (2.5.15)

During the phenotyping visit, clinical information that is collected may impact participant eligibility. All participants in the PI-ME/CFS group will have documentation of being diagnosed with the illness in the community. In this way, PI-ME/CFS participants found not to meet inclusion/exclusion criteria during the phenotyping visit still represents what ME/CFS is in the community. For this reason, PI-ME/CFS participants that are found to have alterative or concomitant diagnoses that would otherwise exclude from study participation may still be invited to complete all of the phenotype visit procedures.

Participants in the HV and COVID-19 HV groups may be found to meet exclusion criteria during Visit 1. Such participants are also permitted to complete Visit 1 procedures, as long as they do not have substantial daily fatigue nor concerns for safety. Samples and data from these participants will be used in the primary analysis. HV and COVID-19 HV participants found to have substantial daily fatigue will have their study participation ended immediately and will not be used in primary analyses. Study participation for HV individuals meeting exclusion criteria will be complete at the end of Visit 1. Study participation for all COVID-19 HV individuals will be complete at the end of Visit 1.

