## 4.6.17 : fMRI

fMRI will be completed during the exercise stress visit and will occur on two separate days, once before and once after the exercise challenge. The following imaging paradigm will be utilized: The subject will lie in the scanner operating a dynamometer to measure the force generated by the muscles of the distal upper limb in a first phase of the scan, and a button box for answering a cognitive test in the second phase of the scan. A structured set of imaging tasks are planned. An optional MRI-compatible electroencephalogram cap may be installed on subject's head before installing the subject in the MRI scanner in order to monitor the cortical activity during fMRI scanning and to allow the measurement of the cortico-muscular coupling during the muscular and cognitive fatiguing exercises. This may add about 30 min to the setup time.

Each scanning session will begin with a localizing image, an anatomical scan, and resting-state BOLD acquisition (20 minutes).

A test of cognitive fatigue will be performed within the MRI environment before the muscular fatigue test. In this study, there will be a sequence of two-choice reaction times. The correct choice will be based on a simple cognitive operation and the difficulty of the operation will not change over the series. Cognitive fatigue will be deemed present if the reaction time increases over the sequence. The test will continue for 10 minutes. fMRI will be done for 10 minutes, and the task analyzed as an event related design. The time between reaction time trials will be jittered, so that the MR signal can be extracted. The behavioral data and the MR data will be related parametrically. Another resting BOLD acquisition will be performed after the cognitive task. Even if no significant learning is expected related to the task, the subjects will get some training on the task prior to the MRI study so the novelty and/or any amount of learning will be further minimized. Subjective appraisals of cognitive fatigue will be measured at intervals during the cognitive fatigue task (20 minutes).

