
We will use a multivariate regression model where the response variable is connectivity strength among regions of interest pre- and post- exercise. Predictors include group status and fatigue scores.

Region of interest for the connectivity analysis will be defined based on tasks 1) and 2). For this, data will be pre-processed with standard techniques using AFNI. Imaging quality assurance will be performed (i.e. motion correction parameters). We will fit a multivariate regression model to detect the differences in activity patterns of each task. Behavior and scales of fatigue will be entered as covariates.

Significance of the results will be set at p = 0.05 corrected for multiple comparisons for all analyses.

Lastly, we will conduct receiver operating characteristic (ROC) analysis for selected markers that are potentially important, which will be identified by exploratory analysis and several statistical approaches mentioned above. We will evaluate the accuracy of each marker for its ability to classify subjects in the PI-ME/CFS group from those in the HV control group. For example, if MRI imaging measurements are significantly different among groups, next, we will calculate the nonparametric area under the ROC curve (AUC) for each imaging marker and its 95% confidence interval.

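### The primary MRI aim is a plain PI-ME/CFS versus HV difference in connectivity, but the only connectivity model adjusts for fatigue, on which the groups were selected

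*Combined protocol and SAP*

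**What the plan says.** Section 12.1 gives the imaging work its own primary aim: "The primary MRI imaging aim is to test whether PI-ME/CFS group has significantly different connectivity patterns compared to the HV control group". Nothing in that sentence holds fatigue constant. The section then describes one model whose response is connectivity strength before and after exercise, and says of it: "Predictors include group status and fatigue scores". It does not name the fatigue scale, when it is scored, any interaction, or the coefficient to be tested. For the task-activity model, which helps define the regions of interest, it says: "Behavior and scales of fatigue will be entered as covariates". No group contrast is stated there.

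Earlier, Section 12.1 has a general rule: "For each continuous-scale outcome, repeated measures analysis of variance (ANOVA) will be used". That rule has no fatigue covariate and does not mention connectivity.

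Fatigue also decides who enters each group. Section 3.2.3 requires cases to have an MFI "score of ≥ 13 on the general fatigue subscale or ≥10 on the reduced activity subscale". Section 3.3.4 excludes healthy volunteers with "Substantial daily fatigue as determined using PROMIS-SF Fatigue: score of > 17". Section 4.5 adds: "HV and COVID-19 HV participants found to have substantial daily fatigue will have their study participation ended immediately". Section 4.6.17 collects further fatigue ratings in the scanner: "Subjective appraisals of cognitive fatigue will be measured at intervals during the cognitive fatigue task". It does the same for the muscular task.

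**The concern.** A regression with group and fatigue as main effects answers this question: among people equally fatigued, does connectivity differ by group? The stated aim asks whether connectivity differs between the groups as they are. The two answers agree only if fatigue has no within-group relation to connectivity or the groups do not differ on the score used. The second condition is unlikely for a trait fatigue score, because one group is chosen for being fatigued and the other for not being so. Where the groups overlap little on fatigue, the comparison at equal fatigue also rests on extrapolation.

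Three later uses are exposed:

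- Section 4.1 will read negative results as showing where large differences are unlikely.
- Section 12.2 will take effect sizes from this study to design a larger one.
- Section 12.1 gives imaging measures that differ significantly among groups as its example of markers to take into an ROC analysis of PI-ME/CFS against HV. That analysis does not adjust for fatigue, so a fatigue-adjusted screen could drop a good classifier or pass a poor one.

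**Working it through.** **The plan's own figure.** Section 12.2 cites 12 subjects for 80% power at a threshold of 0.05 for single-voxel activation. It gives no effect size, SD, sidedness or design, so the figure cannot be reproduced. Solving backwards with a two-sided normal approximation, 12 subjects imply 2.802/√12 = 0.81 SD for one sample. With 12 per group they imply 2.802 × √(2/12) = 1.14 SD. The figure does not concern connectivity and has no bearing on this point.

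**Inputs.** From the documents: 20 per group (Section 12.2) and a 0.05 level (Section 12.1). Assumed:

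- a two-sided test of one contrast, without the multiplicity correction that Section 12.1 requires;
- one fatigue score and no interaction;
- within-group SD of 1 for both connectivity and fatigue;
- a fatigue gap s of 1 to 4 within-group SDs;
- a within-group correlation r between fatigue and connectivity of 0, +0.2 or -0.2.

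The gap cannot be derived. A case can qualify on the reduced-activity subscale instead, and healthy volunteers are screened on a different instrument.

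**Formulas.**

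- Difference detectable with 80% power, without fatigue in the model: d = (1.960 + 0.842) × √(2/20) = 0.886 SD.
- Group coefficient with fatigue in the model: c = d - r·s.
- Its standard error: SE = √(1 - r²) × √[(2/20)(1 + s²/4)].
- Power: Φ(c/SE - 1.96) + Φ(-c/SE - 1.96).

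Example, s = 2 and r = +0.2: c = 0.886 - 0.4 = 0.486; SE = 0.980 × 0.447 = 0.438; c/SE = 1.11; power 20%.

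| Gap s | Variance inflation 1 + s²/4 | r = 0: coefficient, power | r = +0.2 | r = -0.2 |
|---|---|---|---|---|
| 1 | 1.25 | 0.89, 71% | 0.69, 51% | 1.09, 88% |
| 2 | 2.00 | 0.89, 51% | 0.49, 20% | 1.29, 84% |
| 3 | 3.25 | 0.89, 34% | 0.29, 8% | 1.49, 76% |
| 4 | 5.00 | 0.89, 24% | 0.09, 5% | 1.69, 68% |

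At r = +0.2 the coefficient is 23%, 45%, 68% and 90% below 0.886. At r = -0.2 it is above it by the same percentages. The r = 0 column is the pure cost in variance; power there drops below 40% only beyond a gap of about 2.6 SD. The low power at r = +0.2 mostly reflects the changed estimand.

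**Check by simulation.** Least-squares fits to 6,000 data sets per scenario used 20 per group, a total difference of 0.89 SD and gaps of 1, 2 and 3. Without fatigue in the model, the group coefficient averaged 0.88 to 0.90, with power of about 78%. With fatigue added, the average depended on how much of the difference ran with fatigue:

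- none of it: 0.88 to 0.91;
- half of it: 0.44 to 0.46, with power of 28%, 17% and 12%;
- all of it: about 0.00, with rejection in 5% to 6% of runs, close to the null rate.

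A real group difference that follows fatigue would thus be reported as no group difference.

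**The case against.** The strongest reply is that an unadjusted analysis is already in the plan. Connectivity strength is a continuous outcome measured before and after exercise in both groups, and the general ANOVA rule covers every such outcome. The methods are also introduced as some of the relevant ones, so the list is open. On this reading only the order of precedence is unclear. The point is fair, and it means the plan does not rule out the plain contrast. But the regression is the one model written for connectivity, and it sits directly under the MRI aim. Nothing says that the ANOVA decides that aim. If both apply, one aim has two tests with different estimands and no rule for choosing between them.

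Other objections stand in part:

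- The list of predictors is not exhaustive, and a difference at equal fatigue is exact only for a main-effects model. With a group-by-fatigue term, the group coefficient becomes a difference at one chosen fatigue value, which is still not the plain contrast.
- If the score is an in-scanner rating, nobody was selected on it and the gap may be small. The plan does not say which score it is.
- Relating connectivity to fatigue serves the secondary objective in Section 2.2. That supports keeping the model, but not using it to test the primary MRI aim.
- The study is exploratory and no confirmatory decision hangs on this coefficient. Even so, Section 12.1 calls this a primary aim to be tested at a corrected 0.05.

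**Conclusion.** The concern holds. As written, the dedicated connectivity model does not estimate the quantity in the stated aim. That conclusion follows from the text and needs none of the assumed numbers. The size and direction of the error cannot be known from the documents. Over the range shown, the adjusted coefficient runs from 90% too small to 90% too large, and power from 5% to 88%, against 80% without adjustment. These figures rest on the assumed gaps, correlations and effect, one fatigue score and an uncorrected level. They show what could happen and are not a forecast. The remark on the task-activity model is conditional: it matters only if a group contrast from that model is used to choose regions. The mismatch should be fixed, because both effect sizes and negative findings are to be carried forward.

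**What to change.** In Section 12.1, name one model as the test of the primary MRI aim: connectivity on group, time (before and after exercise) and group-by-time, without fatigue scores. State which of its terms decides the aim, and how it relates to the general ANOVA rule. If a group contrast in the task-activity model is used to select regions of interest, run that contrast without fatigue scales as well.

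Keep the fatigue question as a secondary model, for example within PI-ME/CFS, and state the fatigue scale, the time point and the coefficient tested. Label any group coefficient adjusted for fatigue as a difference at equal fatigue, and do not carry it forward as the PI-ME/CFS versus HV effect size.

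The cost is wording in the statistical section and one additional model. No new data are needed. Section 12.3 says that an interim analysis of the ME/CFS and HV cohorts has begun, so this should be settled promptly, and any connectivity result already produced should be marked with the model it came from.
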